### Data Handling Rules for AEs

Duration of AEs will not be calculated if there is missing stop date information.

If the intensity of an AE is unknown, it will be considered as severe. If the relationship to study drug is missing, it will be considered as related.

For relatedness, AEs determined to be 'not related' or 'unlikely related' to study drug will map to 'not related', while all other values will map to 'related'.

## **AE Summaries**

All AE summary tables described in this Section will be produced four ways, ie for each of the following types of AEs:

- a. TEAEs in Part A, based on the SS
- b. TEAEs in Part B prior to flare, based on the SSB
- c. TEAEs in Part B for subjects experiencing a flare, based on the ETS
- d. TEAEs in Part B under CZP full-dose therapy, based on the FD

SAEs will be classified by SOC, High Level Term (HLT), and PT according to MedDRA®. The latest version available to the sponsor at the time of coding will be used. Summary tables will display the number and percentage of subjects experiencing the TEAEs and number of TEAEs. In this style of output, “number of TEAEs” will include all occurrences of a TEAE including repeat occurrences in individual subjects, while “number of subjects” will count each subject only once.

Overall summaries of AEs will be produced to present the number of events and number and percentage of subjects with:

- Any TEAE
- Any serious TEAE
- Any TEAE leading to study discontinuation
- Permanent withdrawal of study medication due to TEAEs
- Any drug-related TEAE
- Any severe TEAE
- All Deaths (AEs leading to death)
- Deaths (TEAE leading to death)

In addition, the following AE summaries will be presented:

- All TEAEs by primary SOC, HLT, and PT (for the Parts/Analysis sets a, b, c, d)
- All serious TEAEs by primary SOC, HLT, and PT (for the Parts/Analysis sets a, b, c, d)
- All TEAEs leading to permanent discontinuation of study drug by primary SOC, HLT, and PT (for the Parts/Analysis sets a, b, c, d)
- All TEAEs leading to death by primary SOC, HLT, and PT (for the Parts/Analysis sets a, b, c)
- All TEAEs by primary SOC, PT, and maximum intensity (for the Parts/Analysis sets a, b, c, d)
- All TEAEs by primary SOC, PT, and maximum relationship (for the Parts/Analysis sets a, b, c, d)

- All serious TEAEs by primary SOC, PT and maximum relationship (for the Parts/Analysis sets a, b, c, d)
- All TEAEs above reporting threshold of 5% by primary SOC and PT (for the Parts/Analysis sets a, b, c, d)
- All non-serious TEAEs above reporting threshold of 5% by primary SOC and PT (for the Parts/Analysis sets a, b, c)
- All injection related TEAEs by primary SOC, HLT, and PT (for the Parts/Analysis sets a, b, c, d)

AE summary tables will also be produced to display the exposure adjusted incidence rate (EAIR) with associated 95% CI, and the exposure adjusted event rate (EAER):

- All TEAEs by primary SOC, HLT, and PT (for the Parts/Analysis sets a, b, c, d)
- All serious TEAEs by primary SOC, HLT, and PT (for the Parts/Analysis sets a, b, c, d)

For EAIR, the numerator will be the total number of subjects experiencing the AE of interest in the corresponding period. The denominator will be 100 patient-years; that is, the total summation of individual patient-years at risk up to the first occurrence of the AE of interest for subjects with that AE, and the total patient-years at risk for those subjects not experiencing that AE, divided by 100. EAIRs will be presented with a 95% exact CI based upon the Chi-Square distribution (Ulm, 1990).

For EAERs, the numerator will be the number of AEs including repeat occurrences in individual subjects; the denominator will be 100 patient-years. That is, the total summation of individual patient-years at risk divided by 100. No CI will be computed for EAER.

The TEAE summary table will be presented by TE ADAb status and depending on the timepoint of onset of TEAE (Prior to becoming ADAb Positive $\geq$ 1024, After becoming ADAb Positive $\geq$ 1024, Subjects Who Never Became ADAb Positive $\geq$ 1024) based on PKSB.)

The following AEs of interest will be summarized:

1. Serious infections, including opportunistic infections
2. Malignancies, including lymphoma
3. Serious cardiovascular events (i.e. Major adverse cardiac events or MACE)
4. Congestive heart failure
5. Demyelinating-like disorders
6. Aplastic anemia, pancytopenia, thrombocytopenia, neutropenia, and leucopenia
7. Serious bleeding events
8. Lupus and lupus-like illness
9. Serious skin reactions (eg, Stevens Johnson Syndrome, toxic epidermal necrosis, and erythema multiforme)

Serious infections (1) will be summarized using the previously described serious TEAEs tables. No separate tables will be produced. In addition, summary tables will be produced for

opportunistic infections (including tuberculosis). Identification of opportunistic infections (including tuberculosis) will be performed using UCB-defined search criteria based on a two step process using identification via predefined list of PTs in addition to identification via manual review by the study physician.

(2) will be presented in two set of summary tables using the criteria standard MedDRA® query (SMQ) = “Malignant or unspecified tumours” and SMQ=“Malignant tumours”, respectively. The SMQ search will include all TEAEs which code to a PT included in the Scope=Narrow group within each SMQ. Corresponding summary tables will also include incidence of “Any malignancy (including unspecified, excluding non-melanomic skin cancers)” or “Any malignancy (excluding non-melanomic skin cancers)” depending on the table.

(3) will be presented in a stand-alone table and will be identified using the following UCB-defined search criteria:

- All serious TEAEs which code to a PT included in the search=Broad and/or Narrow scope of the following SMQs:
  - Haemorrhagic central nervous system vascular conditions (SMQ)
  - Ischaemic central nervous system vascular conditions (SMQ) except events coding to PT “Transient ischaemic attack”
- All serious TEAEs which code to a PT included in the HLT “Ischaemic coronary artery disorders” except events coding to PT “Chest Pain” or “Chest discomfort”
- All serious TEAEs which code to a PT included in any of the following HLTs: “Heart Failures NEC”, “Left Ventricular Failures”, or “Right Ventricular Failures” and which also code to the SOC of “Cardiac Disorders” as Primary SOC.

(4) will be manually identified by the study physician from the previously described any TEAEs tables. No separate tables will be produced.

(5) will be presented in a stand-alone table which is based on the SMQ = “Demyelination”. The SMQ search should include all TEAEs which code to a PT included in Scope=Narrow group within the SMQ. TEAEs which code to a PT included in the Scope=Broad group within the SMQ should be excluded from the search.

(6) will be presented in tables using the criteria SMQ = “Haematopoietic cytopenias” in the subset of Serious TEAEs. The SMQ search will include all serious TEAEs which code to a PT included in the Scope=Broad and/or Scope=Narrow groups within the SMQ.

(7) will be presented in tables using the criteria SMQ = “Haemorrhage terms (excl laboratory terms)” in the subset of serious TEAEs. The SMQ search will include all serious TEAEs which code to a PT included in the SMQ. Note that there is only a Narrow scope defined for this SMQ.

(8) will be manually identified by the study physician from the previously described any TEAEs tables. No separate tables will be produced.

(9) will be manually identified by the study physician from the previously described any serious TEAEs tables. No separate tables will be produced.

In addition, while not considered to be AEs of interest, following types of events will also be summarized:

- Hepatic events
- Hypersensitivity reactions and anaphylactic reactions

Hepatic events will be identified in the set of all TEAEs using following SMQs:

- Cholestasis and jaundice of hepatic origin (SMQ);
- Hepatic failure, fibrosis, and cirrhosis and other liver damage-related conditions (SMQ);
- Hepatitis, non-infectious (SMQ);
- Liver-related investigations, signs and symptoms (SMQ);
- Liver-related coagulation and bleeding disturbances (SMQ)

Hypersensitivity reactions and anaphylactic reactions will be summarized together.

Corresponding set of tables will include incidence of following types of events:

- Any hypersensitivity and anaphylactic reactions
- Any hypersensitivity reactions
- Any anaphylactic reactions

All TEAEs that emerge within one day of when a study medication injection reaction was received which code to the following PTs will be considered to be a hypersensitivity reaction and included in the summary tables:

- Administration site hypersensitivity
- Documented hypersensitivity to administered product
- Drug hypersensitivity
- Hypersensitivity
- Hypersensitivity vasculitis
- Infusion site hypersensitivity
- Injection site hypersensitivity
- Medical device site hypersensitivity
- Type II hypersensitivity
- Type IV hypersensitivity reaction

Injection reactions are identified by the investigator on the eCRF.

An algorithmic approach will be used to identify TEAEs that are considered to be anaphylactic reactions. PTs are separated into the 4 distinct categories (A, B, C, D) prior to the algorithmic approach being applied.

All TEAEs that emerge within one day of when a study medication injection reaction was received, and which fulfill any of the following 3 criteria will be included in the summary tables:

- If a subject reports any TEAE which codes to a PT included in Category A, then the event will be flagged as an anaphylactic reaction and summarized as such in the tables.

- If a subject reports any TEAE which codes to a PT included in Category B and reports any TEAE which codes to a PT included in Category C, and both TEAEs have the same start date, then both events will be flagged as anaphylactic reactions and summarized as such in the tables.
- If a subject reports any TEAE which codes to a PT included in Category D and reports (either a TEAE which codes to a PT included in Category B or a TEAE which codes to a PT included in Category C), and both TEAEs have the same start date, then both events will be flagged as anaphylactic reactions and summarized as such in the tables.

Category A consists of the following PTs which are included in the SMQ = Anaphylactic reaction (SMQ):

- Anaphylactic reaction
- Anaphylactic shock
- Anaphylactic transfusion reaction
- Anaphylactoid reaction
- Anaphylactoid shock
- Circulartory collapse
- Dialysis membrane reaction
- Kounis syndrome
- Shock
- Shock symptom
- Type I hypersensitivity

Category B consists of the following PTs:

- Acute respiratory failure
- Asthma
- Bronchial oedema
- Bronchospasm
- Cardio-respiratory distress
- Chest discomfort
- Chocking
- Chocking sensation
- Circumoral oedema
- Cough
- Cyanosis

This document contains trade secret information and is intended to support any marketing authorization application and any extensions or variations thereof.  
REDACTED COPY

- Dyspnoea
- Hyperventilation
- Irregular breathing
- Laryngeal dyspnea
- Laryngeal oedema
- Laryngospasm
- Lyngotracheal oedema
- Mouth swelling
- Nasal obstruction
- Oedema mouth
- Oropharyngeal spasm
- Oropharyngeal swelling
- Respiratory arrest
- Respiratory distress
- Respiratory dyskinesia
- Respiratory failure
- Reversible airways obstruction
- Sensation of foreign body
- Sneezing
- Stridor
- Swollen tongue
- Tachypnoea
- Throat tightness
- Tongue oedema
- Tracheal obstruction
- Tracheal oedema
- Upper airway obstruction
- Wheezing

Category C consists of the following PTs:

- Allergic oedema
- Angioedema

This document contains information used to support any marketing authorization application and any extensions or variations thereof.  
REDACTED COPY

- Erythema
- Eye oedema
- Eye prutitus
- Eye swelling
- Eyelid oedema
- Face oedema
- Flushing
- Generalised erythema
- Injection site urticarial
- Lip oedema
- Lip swelling
- Nodular rash
- Ocular hyperaemia
- Oedema
- Periorbital oedema
- Pruritus
- Pruritus allergic
- Pruritus generalized
- Rash
- Rash erythematous
- Rash generalized
- Rash pruritic
- Skin swelling
- Swelling
- Swelling face
- Urticaria
- Urticaria papular

Category D consists of the following PTs:

- Blood pressure decreased
- Blood pressure diastolic decreased
- Blood pressure systolic decreased

This document contains information used to support any marketing authorization application and any extensions or variations thereof.  
REDACTED COPY

- Cardiac arrest
- Cardio-respiratory arrest
- Cardiovascular insufficiency
- Diastolic hypotension
- Hypotension

The following AE summary tables (for the Parts/Analysis sets a, b, c, d) will be used as the basis for presentation of AEs of interest as well as for hepatic events, hypersensitivity reactions and anaphylactic reactions:

- All TEAEs by primary SOC, HLT, and PT (applies to opportunistic infections [1], [2], hepatic events, hypersensitivity reactions and anaphylactic reactions)
- All serious TEAEs by primary SOC, HLT, and PT (applies to [3], [5], [6] and [7])

EAIR and EAER will be calculated and included in these summary tables of AEs of interest.

Finally, a summary of all TEAEs which emerged at any time during the study (Part A or Part B) while on CZP 200mg Q2W will be produced. This summary will include all subjects in the SS and all subjects in the SSB who received CZP 200mg Q2W during Part B (either as randomized treatment or as escape treatment). EAIR and EAER will be calculated and included in this summary table.

TEAEs which emerged at any time during the study while on CZP 200mg Q2W will be defined as follows:

- In subjects not randomized into Part B, TEAEs under CZP full-dose therapy will be defined as all AEs starting on or after the date of first CZP full-dose therapy in Part A and up to 70 days after the last dose of study medication in Part A.
- In subjects randomized into Part B to the PBO or CZP 200mg Q4W arm who do not experience a flare and do not escape to CZP full-dose therapy, TEAEs under CZP full-dose therapy will be defined as all AEs starting on or after the date of first study medication in Part A and up to 70 days after the last dose of study medication in Part A and before the date of the first study medication in Part B.
- In subjects randomized into Part B to the PBO or CZP 200mg Q4W arm who do experience a flare and do escape to CZP full-dose therapy, TEAEs under CZP full-dose therapy will include all post-flare TEAEs in Part B.
- In subjects randomized into Part B to CZP 200mg Q2W arm, TEAEs under CZP full-dose therapy will include all TEAEs in Part A and Part B.

AE data will be listed. A glossary for the AE listing will detail the verbatim terms that are coded to each SOC, HLT, and PT.

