## **10 SAFETY ANALYSES**

### **10.1 Extent of exposure**

#### **10.1.1 Part A**

Exposure to study medication in Part A will be evaluated by summarizing the total number of CZP injections, the total amount of CZP received in mg, the total drug exposure duration in days, the patient time at risk and the total patient years at risk. Summaries will be based on the SS and presented by axSpA subpopulation and overall.

Duration of exposure to study medication in Part A will be calculated (in days) as:

- The date of the last Part A injection – date of first Part A injection + 14 days.

If the first study medication administration in Part B, final contact date or death occurs prior to the completion of the 14-day period, exposure to study medication in Part A will be censored at the earliest of these events.

Patient time at risk in Part A will be calculated (in days) as:

- The date of the last injection in Part A – date of first injection in Part A + 70 days

If the first study medication administration in Part B, final contact date or death occurs prior to the completion of the 70-day period, patient time at risk in Part A will be censored at the earliest of these events.

Total patient years at risk will be calculated as the sum of all the relevant patient time at risk (in days) divided by 365.25.

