- The date of the last CZP 200mg or PBO Part B injection prior to start of escape full-dose CZP – date of Week 48 injection + 70 days for subjects in the 200mg CZP Q2W and PBO groups [3]
- The date of the last CZP 200mg Part B injection prior to start of escape full-dose CZP – date of Week 48 injection + 70 days for subjects in the 200mg CZP Q4W group [3]

If the final contact date or death occurs prior to the completion of the 70-day period for [1] or [2], patient time at risk in Part B will be censored at the earliest of these events. If the start of escape full-dose CZP occurs prior to the completion of the 70-day period for [3] and [4], patient time at risk in Part B will be censored at the date of this event.

Total patient years at risk will be calculated as the sum of all the relevant patient time at risk (in days) divided by 365.25.

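### The adverse event table split at ADAb titre 1024 has no person-time to match its columns, so they would differ through observation time even with no antibody effect

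*SAP*

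**What the plan says.** The AE Summaries part of SAP Section 10.2 gives this table one sentence: "The TEAE summary table will be presented by TE ADAb status and depending on the timepoint of onset of TEAE". The sentence lists three onset categories: before reaching a titre of 1024 or more, after reaching it, and "Subjects Who Never Became ADAb Positive" at that level. The population is the PKSB, that is, subjects treated in Part B with at least one PK sample in Part B. The sentence does not say which statistic is shown or which study period is covered.

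The general content rule earlier in the same part is: "Summary tables will display the number and percentage of subjects experiencing the TEAEs and number of TEAEs". Rates come in a separate list: "AE summary tables will also be produced to display the exposure adjusted incidence rate (EAIR) with associated 95% CI, and the exposure adjusted event rate". That list has two entries, all TEAEs and "All serious TEAEs by primary SOC, HLT, and PT (for the Parts/Analysis sets a, b, c, d"), where a to d are the Part A safety set, the Part B safety set, the escape therapy set and the Part B full-dose set. Later in Section 10.2, EAIR and EAER are also assigned by name to the AE-of-interest tables and to the whole-study CZP Q2W table.

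The EAIR denominator is "the total summation of individual patient-years at risk up to the first occurrence of the AE of interest for subjects with that AE", and total patient-years for the other subjects. Section 10.1 defines time at risk by study part, escape and full-dose exposure. In Part A the stated censoring is: "If the first study medication administration in Part B, final contact date or death occurs prior to the completion of the 70-day period". In Part B before flare it is: "If the start of escape full-dose CZP occurs prior to the completion of the 70-day period".

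**The concern.** The before and after columns divide one subject's follow-up between them, while the never column holds a subject's whole follow-up. A percentage of subjects, or a raw event count, depends on how long subjects could be observed in that column. With no matching person-time, the table mixes any effect of antibodies on safety with the date on which subjects reached the titre.

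This matters because no other table in the current SAP relates ADAb to adverse events. The outcome summary by titre in Section 9.2 covers only flare and ASDAS-MI. Adjacent before and after columns invite the reader to set them side by side.

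**Working it through.** The SAP gives no figure for this table, so there is none to reproduce. The check has two parts.

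**1. Is there a person-time rule for these columns?**

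| Place in SAP | What it defines | Cut at the date titre 1024 is reached? |
|---|---|---|
| 10.1.1 to 10.1.3 | Time at risk by part, escape and full-dose exposure | No |
| 10.2, EAIR | Patient-years to first AE, otherwise total | No |
| 10.2, EAER | Total patient-years | No |
| 9.2 | Subject class by highest titre; Kaplan-Meier of time to TE ADAb positivity | No AE person-time |

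None of the tables assigned EAIR or EAER by name is the PKSB table.

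**2. How large is the effect under no antibody effect?**

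Input from the SAP: Section 2.3.4 puts the last planned double-blind dose at Week 94, and TEAEs count up to 70 days (10 weeks) after the last dose. That gives 94 + 10 = 104 weeks for a non-flaring randomised subject, if the table spans both parts.

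Assumptions, not in the SAP: a constant hazard that is the same before, after and never; 0.5 to 2.0 TEAEs per patient-year; conversion at Week 12, 24, 48 or 72.

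Formula: P(at least one TEAE) = 1 − exp(−rate × weeks / 52.18). With conversion at week w, the weeks are w (before), 104 − w (after) and 104 (never).

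Worked case, 1.0 per patient-year, w = 24:
- before: 1 − exp(−24/52.18) = 36.9%
- after: 1 − exp(−80/52.18) = 78.4%
- never: 1 − exp(−104/52.18) = 86.4%

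| Rate per patient-year | Conversion week | Before | After | Never |
|---|---|---|---|---|
| 1.0 | 12 | 20.5% | 82.8% | 86.4% |
| 1.0 | 24 | 36.9% | 78.4% | 86.4% |
| 1.0 | 48 | 60.1% | 65.8% | 86.4% |
| 1.0 | 72 | 74.8% | 45.8% | 86.4% |
| 0.5 | 24 | 20.5% | 53.5% | 63.1% |
| 2.0 | 24 | 60.1% | 95.3% | 98.1% |

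The order of before and after reverses between Week 48 and Week 72. Raw counts behave the same way: at 1.0 per patient-year and Week 24, 100 subjects give 46 / 153 / 199 events.

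**If the table is read as carrying rates.** With the undivided patient-years of Section 10.1, 100 converters contribute 100 × 104/52.18 = 199 patient-years to both the before and the after column. The EAER would be 46/199 = 23 and 153/199 = 77 per 100 patient-years, against 199/199 = 100 for never. With time split at conversion, the three are 46/46, 153/153 and 199/199, each 100 per 100 patient-years, which is the assumed rate.

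**If the table covers Part B only.** The window is 56 weeks (Week 48 to Week 94, plus 10). Conversion at Week 72 leaves 24 weeks before, 32 after and 56 for never, giving 36.9% / 45.8% / 65.8% at 1.0 per patient-year. Subjects who converted in Part A have no before time at all.

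**The case against.** The strongest objection is that the sentence names no statistic. Counts and percentages are inferred from a general rule in a part of the SAP built around sets a to d, and the PKSB is none of these. The sentence also directly follows the EAIR and EAER definitions, so rates may have been meant. It is fair that the statistic is inferred. The gap remains, because rates for the before and after columns cannot be computed correctly from the time at risk as defined.

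The table is also descriptive. The SAP says it is presented; no test or conclusion is attached, and exposure-adjusted rates are already planned for the main safety tables. This limits the weight of the point.

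Two stronger readings are tempting and not supported. A reader might infer that the columns differ by observation time alone. The SAP supports only that they would differ even with no antibody effect; a real effect could add to this or offset it. A reader might also infer that the never column must show the highest percentage whatever antibodies do. That holds only under the assumed null. With conversion at Week 24, the after column exceeds never once the post-conversion rate ratio passes 104/80 = 1.3. At a ratio of 2 it is 1 − exp(−2 × 80/52.18) = 95%, against 86%.

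Finally, splitting person-time equalises the columns under no effect only if the hazard is otherwise constant. Treatment changes at Week 48, when subjects are randomised to three arms including placebo, so before and after can still differ by treatment and period. This stands, and the fix has to deal with it.

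**Conclusion.** The point holds as a minor one. As written, the table sets unequal observation periods side by side with no person-time to match, and either reading of its content leaves that gap. The illustration (about 37% / 78% / 86% for conversion at Week 24, and 75% / 46% / 86% at Week 72) shows that the direction of the before-after difference can be set by conversion time alone when there is no effect. The sizes rest on an assumed 1 TEAE per patient-year, a constant hazard, assumed conversion weeks and a 104-week window; the SAP states neither the event rate nor the table's period. The qualitative result does not depend on these values. The table is one descriptive safety display in randomised subjects, and nothing in the efficacy conclusions rests on it.

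**What to change.** In Section 10.2, specify the table as follows:

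- State the study period it covers.
- Reconcile the titre cut. Sections 4.7 and 10.2 use 1024 or more, while Section 9.2 places 1024 itself in the middle class and makes the top class above 1024.
- Split each subject's time at risk at the sampling date of the first qualifying titre. Converters' time before that date goes to the before column, later time to the after column, and all time of the other subjects to never.
- Report patient-years, EAIR with 95% CI and EAER for each column, and say whether a converter with an event before the split is at risk again for the EAIR after it.
- Present the table by treatment group or study part, because treatment changes at Week 48.
- Add a note that raw percentages are not comparable across columns.

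The cost is SAP wording and one extra derivation from dates already collected. The downside is that conversion is dated to a sampling visit, so a little time and a few events will be assigned to the wrong side of the split.

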### **4.3 Interim analyses and data monitoring**

Main focus of this interim analysis will be the efficacy and safety up to Week 48. An interim freeze of the database will be performed once all subjects have completed Week 48 of Part A. Part A data will be reported in corresponding Part A tables and listings. All blinded data will remain blinded. In the disposition tables, treatment will remain blinded and be presented according to a dummy treatment assignment for Part B. For the listing only open-label data from Part A will be included. The purpose of the interim analysis is to check whether the assumptions on efficacy of CZP made for the protocol were correct, and to potentially present the results at scientific meetings. No CSR will be written. The following assessments will not be included in the Interim Analysis:

- MRI Efficacy scores (SPARCC (Sacroiliac joint), Spine ASspiMRI-a in Berlin Modification score)
- Work Productivity Questionnaire
- EQ-5D-3L
- Fecal and serum calprotectin
- Correlation between calprotectin and IBD, CRP
- SF36 (domains, PCS, MCS)
- Resource utilization
- PK
- ADAb

The scope of the Interim Analysis will not be covered in a separate Analysis Plan.

No specific data monitoring, steering, or evaluation committee is planned for this study.

The following variable will be classed as unblinding during the full study. Therefore, these variables will be kept blinded until study unblinding after database lock:

- Randomized treatment group
- CRP (Post Week 48)
- MRI Efficacy scores (Post Week 48)
- PK and ADAb (Post Week 48).

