- The date of the last Part A full-dose CZP injection – date of first Part A full-dose CZP injection + 70 days for subjects not randomized into Part B. Patient time at risk will be censored at the date of earliest of the following events if any of these events occur prior to the completion of the 70-day period: final contact or death.
- The date of the last Part A full-dose CZP injection – date of first Part A full-dose CZP injection + 70 days for subjects randomized into Part B to the PBO or CZP 200mg Q4W arms who do not experience a flare and do not escape to CZP full-dose therapy. Patient time at risk will be censored at the date of earliest of the following events if any of these events occur prior to the completion of the 70-day period (first study medication administration in Part B, final contact or death).
- The sum of (date of the last Part A full-dose CZP injection – date of first Part A full-dose CZP injection + 70 days) [1] and (date of the last escape full-dose CZP injection – date of first escape full-dose CZP injection + 70 days) [2] for subjects randomized into Part B to the PBO or CZP 200mg Q4W arms who do experience a flare and do escape to CZP full-dose therapy. If first study medication administration in Part B occurs prior to the completion of the 70-day period for [1], [1] will be censored at the date of this event. If final contact or death occurs prior to the completion of the 70-day period for [2], [2] will be censored at the date of the earliest event.
- The date of the last Part B injection – date of first Part A full-dose CZP injection + 70 days for subjects randomized into Part B to CZP 200mg Q2W arm. If final contact or death occurs prior to the completion of the 70-day period, the patient time at risk will be censored at the date of the earliest event.

Total patient years at risk will be calculated as the sum of all the relevant patient time at risk (in days) divided by 365.25.

Exposure data will be listed.

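### AEs of interest 4, 8 and 9 are picked by hand from aggregate tables, with no preset search and no category row, so the planned tables give no reproducible count or EAIR for them

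*SAP*

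**What the plan says.** SAP section 10.2 lists nine AEs of interest and says they are to be summarized. It then sets out, item by item, how each is found.

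- Item 4 (congestive heart failure): "4) will be manually identified by the study physician from the previously described any TEAEs tables. No separate tables will be produced".
- Item 8 (lupus and lupus-like illness): "8) will be manually identified by the study physician from the previously described any TEAEs tables. No separate tables will be produced".
- Item 9 (serious skin reactions): "9) will be manually identified by the study physician from the previously described any serious TEAEs tables. No separate tables will be produced".

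No standard MedDRA query (SMQ), high level term (HLT), preferred term (PT) list or case definition is attached to any of the three. Item 9 names three conditions, but only as examples.

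For the EAIR, time at risk is "the total summation of individual patient-years at risk up to the first occurrence of the AE of interest for subjects with that AE", plus full time at risk for subjects without the event. On the sets: "All AE summary tables described in this Section will be produced four ways", namely Part A (a), Part B before flare (b), flared subjects (c) and full-dose CZP in Part B (d). Subject-level data are available: "AE data will be listed" (section 10.2) and "Exposure data will be listed" (section 10.1.3). On randomized group and certain other variables, section 4.3 says "these variables will be kept blinded until study unblinding after database lock".

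**The concern.** An AE of interest is named in advance so that the report can state, per group, how many subjects had it and at what rate. For these three items the grouping of terms is left to one person's reading of aggregate tables. Two physicians could group the same rows differently, and the SAP gives no means of deciding between them. No planned output shows the resulting count or rate.

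A second issue concerns Part B. The tables are split by treatment group, so selection made from them could be influenced by the arm. At stake is the reproducibility of descriptive safety statements on heart failure, lupus-like illness and serious skin reactions.

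**Working it through.** The SAP gives no figure to reproduce here, so the check compares the provisions of section 10.2 with each other.

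**Step 1: how each item is found, and whether it appears in the closing lists of AE-of-interest tables, which carry EAIR and the exposure-adjusted event rate (EAER).**

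| Item | How found | In the closing lists? |
|---|---|---|
| 1, opportunistic infections | Preset PT list plus physician review | Yes, all TEAEs |
| 1, serious infections overall | Read from the general serious-TEAE tables | No separate table, but not described as hand-picked |
| 2, malignancies | Two SMQs, narrow scope | Yes, all TEAEs |
| 3, serious cardiovascular events | SMQs and HLTs | Yes, serious TEAEs |
| 4, congestive heart failure | Physician, from any-TEAE tables | No |
| 5, demyelinating-like disorders | One SMQ, narrow scope | Yes, serious TEAEs |
| 6, cytopenias | One SMQ | Yes, serious TEAEs |
| 7, serious bleeding | One SMQ | Yes, serious TEAEs |
| 8, lupus-like illness | Physician, from any-TEAE tables | No |
| 9, serious skin reactions | Physician, from serious-TEAE tables | No |

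So 3 of 9 items have neither a preset search nor a category table.

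**Step 2: can a category result be read off the general SOC/HLT/PT tables?** Those tables do carry n (%), EAIR and EAER by row. Suppose a category covers rows j = 1, …, k, with n_j subjects in row j.

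- Subject count: each subject counts once per row but may appear in several rows. The number of distinct subjects D therefore satisfies max(n_j) ≤ D ≤ Σ n_j, and the rows do not fix D.
- EAIR: if T_ij is subject i's time at risk up to the first event in row j (or full time at risk if there is none), row j uses Σ_i T_ij as its denominator. The category needs Σ_i min_j(T_ij), which requires subject-level dates.

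The rows suffice only when the whole category lies in one row, or when at most one of its rows is non-zero. The SAP does not define any of the three items as a single HLT or PT.

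**Step 3: can it be built from the listings?** Yes, once someone decides which terms belong. The AE and exposure listings settle the overlap exactly for any chosen grouping. What the SAP lacks is the grouping.

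**Step 4: is heart failure already covered under item 3?** In part. Item 3 has a preset search on three HLTs (Heart Failures NEC, Left Ventricular Failures, Right Ventricular Failures) with Cardiac Disorders as primary SOC. It takes serious events only and is reported with central nervous system vascular and coronary events, so it yields no item 4 result. It does show that a preset search was to hand.

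**Step 5: is the arm visible at selection?** Section 3.1 presents Part B summaries by treatment group, and section 3.7 does so for flared subjects by randomized group. Under section 4.3, tables bearing the real arms can exist only after unblinding. Section 10.2 does not say whether the physician works from those tables or from an earlier blinded version.

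- Set a is open-label, so only reproducibility is in question.
- Set d contains only full-dose CZP.
- In set c, post-flare events occur on full-dose CZP in every arm.
- The risk therefore bears mainly on pre-flare Part B events, set b above all.

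**The case against.** The strongest reply is that the SAP does what it says. It undertakes to summarize nine items and then states that three will be read from existing tables. The EAIR sentence defines the rate for whatever row is tabulated and does not promise a category rate. Amendment 1 (section 12.3, Changes #33 and #34) moved item 5 from manual identification to an SMQ table, and items 4, 8 and 9 are still manual in the current text, which suggests a choice rather than an oversight. Physician review is also accepted for opportunistic infections. Much of this stands: there is no internal contradiction and no broken promise. But for opportunistic infections the review supplements a preset list, whereas here it stands alone. The item 5 change shows that the sponsor found such a conversion feasible.

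A reader might infer that cases are to be selected with the treatment arm in view. The SAP does not say so. It gives no timing. It uses dummy treatment assignments for the interim disposition tables (section 4.3) and provides for a blinded data evaluation meeting (section 5.2). Arm-aware selection is a possibility left open, no more.

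A reader might also try to size the gap for heart failure from the bounds on D across the three HLTs. That bound depends on counts the SAP cannot supply, uses HLTs that the SAP does not assign to item 4, and says nothing about items 8 and 9. It should not be quoted as a magnitude.

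The protocol, not at hand, may define these conditions. For these three items, however, section 10.2 does not point to it, and it sets out the searches for items 2, 3, 5, 6 and 7 itself.

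**Conclusion.** The point holds as a minor one. Items 4, 8 and 9, 3 of the 9 AEs of interest, rest on unstructured physician review of aggregate tables, and the planned outputs give no reproducible category-level subject count or EAIR for them. Whether the review is blinded is unstated.

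The effect is confined to descriptive safety reporting. It shows only where two or more relevant rows are non-zero or where a term is open to judgement. Row-level n (%), EAIR and EAER, the subject listings, the preset search for serious heart failure under item 3, and the primary analysis are all unaffected. No event counts are assumed. The conclusion rests on the text of section 10.2 and on there being no preset definition that the SAP fails to cite.

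**What to change.** Use for all three items the two-step process already specified for opportunistic infections.

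- **Item 4:** apply the three heart-failure HLTs named under item 3, with Cardiac Disorders as primary SOC, to all TEAEs. Add blinded physician review for relevant terms coded elsewhere. Add [4] to the all-TEAE line in the closing list of AE-of-interest tables, so that EAIR and EAER follow.
- **Items 8 and 9:** fix a PT list before unblinding. For item 9, start from Stevens Johnson Syndrome, toxic epidermal necrosis and erythema multiforme, and restrict to serious TEAEs. Add blinded physician review of subject-level AE listings, and report one pooled row per item with EAIR and EAER.
- **Timing:** state in section 10.2 that the review is completed before unblinding.

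Blinded review alone would not be enough for items 8 and 9, because the grouping would still be unstructured judgement; the PT list is what makes it reproducible.

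Cost: 1 table × 4 sets = 4 outputs for item 4; 2 rows × 4 sets = 8 rows for items 8 and 9; drawing up the PT lists; and one blinded listing review before unblinding.
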